6.4 Accountability Procedures for the Study Product

The PI's local study team will prepare the IPPs and label them with sequential IPP IDs for each practice as well as the practice ID. The IPPs will include the study product. The PI will then mail the IPPs to each of the participating practices with tracking numbers; shipment will be tracked by the PI's study team. The IPPs will include a paid return envelope for the practices to mail back the leftover study product to the PI, with the instruction to return the whole amount of leftover product to the PI when the 6-week reevaluation visit for all patient participants within a practice has been completed. The PI will then safely dispose of the leftover product in a biohazard bin.

6.5 Assessment of Patient participant Compliance with Study Product Administration

Patient participants will be asked to return the medication vials to the dental office at their next visit (6-week re-evaluation) upon completion of the antibiotic / placebo regimen, at which time the practitioner will perform and record a capsule count and will safely store any unused capsules (see additional instruction in Section 6.4 above). For fidelity monitoring regarding compliance with product administration, patient participants will also receive a text inquiry regarding the number of remaining capsules in each bottle on day 10 and reminded to return the medication vials to the office at the reevaluation (6 week) visit. The text response will be recorded by NCC and in case of a discrepancy between self-reported and practitioner-assessed capsule counts, the practitioner-assessed count will be considered as final data. If the patient participant misses returning their bottle at the re-evaluation visit, then a self-reported capsule count will be used for data entering. The training slides will emphasize the need to schedule the second baseline visit within 10 days of initial medication dispensing to ensure antibiotic coverage. Data may be collected within a 30-day time frame from initial medication dispensing, this will not be a protocol violation. If the second baseline visit occurs beyond 30 days from the time of the antibiotic / placebo administration, then the patient participant will be withdrawn from the study. The number of remaining capsules will be recorded, and all patient participants will be analyzed in the originally randomized group consistent with Intention-To-Treat (ITT) analyses principles.

6.6 Concomitant Medications/Treatments

Amoxicillin and/or Metronidazole may interact with other antibiotics, alcohol, disulfiram, and warfarin to cause adverse events. Practitioners will receive training to advise the patient participants during enrollment regarding the potential of interactions and discuss prohibited medications based on known contraindications (e.g., Lithium, disulfiram as well as substances such as alcohol). Patient participants taking the concomitant medications listed above will be excluded from the study (see exclusion criterion #4) prior to enrollment. Patient participants will also be advised to refrain from initiating a prohibited medication during the 10 days of the antibiotic intervention. After the 10-day intervention, the risk of an adverse event from a concomitant medication is extremely low. Therefore, concomitant medications/treatments will not be tracked for research purposes. No rescue medications will be given in this study.

6.7 Study Procedural Intervention(s) Description and Administration

The procedural intervention in this trial is SRP. As described above, SRP entails the mechanical debridement of the root surfaces of teeth as part of periodontal treatment (Badersten et al. 1981). The same procedural intervention will be applied to both arms by operators who will be blinded to the arm allocation of each patient participant. Based on state licensure and routine clinical practice of each dental practice site the SRP may be performed by either the dentist practitioner or by their hygienist. The "PAAS Baseline Visit Checklist" will capture data on whether a dentist or hygienist is completing the visit.

In the training slides it is suggested that all SRP procedures are performed with local dental anesthesia or Topical anesthetic (e.g., Oraqix); this information will be also captured in the "PAAS Baseline Visit Checklist". Adequate completion of SRP will be determined with an appropriate calculus explorer as per standard clinical procedures, and relevant training is provided in the training videos. The intervention will be applied once at each involved quadrant either at the baseline visit or the optional second baseline visit with at least one quadrant completed at the first visit. The drug / placebo loading dose will be performed prior to SRP for the 1st baseline visit, regardless of the number of baseline visits. The second baseline visit should occur within 10 days of the initial baseline visit. If the second baseline visit has not happened within 30 days from initiation of the investigational product (drug / placebo), the patient participant is discontinued from study, and this will be considered as missing data.

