5.5 Patient participant Withdrawal or Discontinuation from Study Procedures/Intervention

5.5.1 Reasons for Patient participant Withdrawal or Discontinuation from Study Procedures/Intervention

Patient participants are free to withdraw from participation in the study at any time upon written request.

Patient participants may choose to discontinue the intervention or study procedures but continue to be followed for treatment in the practice.

The PI's study team may discontinue an individual's participation in an intervention but continue to be enrolled and provide trial data if:

- Any clinical adverse event (AE) or other medical condition or situation occurs such that continued participation in the intervention would not be in the best interest of the patient participant.
- The patient participant meets an exclusion criterion (either newly developed or not previously recognized).

The PI's study team may withdraw a patient participant from the study if:

- The patient participant fails to maintain appointments within a reasonable timeframe, i.e. If the second baseline visit has not happened within 30 days from the time of medication the patient participant is discontinued from study, and this will be considered as missing data.
- The patient participant can no longer be contacted, or patient participant has moved.

5.5.2 Handling of Patient participant Withdrawals from Study or Patient participant Discontinuation of Study Intervention

In the event that a patient participant chooses to withdraw or is withdrawn from the study, a patient participant termination form will be used to capture the date and reason for the withdrawal with no additional study data recorded. Patient participants who are withdrawn may continue to receive routine clinical care as a patient of record for the

treating dentist, but additional study data will not be collected. Data collected prior to study withdrawal will be used for the intention-to-treat analysis.

In the event that the intervention is discontinued, e.g., patient participant develops a persistent drug-related symptom such as diarrhea, prior to completing the intervention, the patient participant will continue to be enrolled in the study and the deviation from the intervention plan will be noted.

Patient participants who are withdrawn from the study after randomization will not be replaced.

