12.4 Final Analysis Plan

Analysis Population: All analyses will be intent-to-treat, i.e., all participants who provide data at baseline will retain their original assignment regardless of the treatment received. All statistical tests will be evaluated using a two-tailed alpha level of .05 and will express precision using 95% confidence intervals.

Center Effects: The Primary analysis will account for variation between centers using a mixed effects model. The empirical Bayes estimate of center effects resulting from this model will be analyzed to assess the degree of heterogeneity between centers by assessing the magnitude of the variance of the random effects. This assessment will consist of a formal statistical test to determine if the variance of the random effect is greater than zero as well as an assessment of its estimated magnitude. If a clinically meaningful amount of variability between centers is detected, exploratory analyses will be conducted to attempt to identify covariates related to center effects including

geographic information, demographic information, and disease-related information. If these analyses identify meaningful subgroups among the centers, subgroups of sites will be created based on the potential for differential effectiveness. These subgroup analyses will be considered secondary and will be conducted in a manner identical to the primary analysis provided that the subgroups are of sufficient size to merit such an analysis. The specific data related to the characteristics of these subgroups, should they prove to exist, will be reported separately.

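### The 30-day rule for the second SRP visit withdraws randomised, dosed participants from follow-up and so creates avoidable missing outcomes that undermine the intention-to-treat aim

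*Protocol*

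**What the plan says.** Section 6.7 gives the target for a needed second visit: "The second baseline visit should occur within 10 days of the initial baseline visit". If that visit has not taken place by day 30, counted from the start of study product, "the patient participant is discontinued from study, and this will be considered as missing data".

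Section 6.5 treats a visit inside 30 days as no violation. Beyond 30 days, "then the patient participant will be withdrawn from the study". The same paragraph ends by saying that "all patient participants will be analyzed in the originally randomized group consistent with Intention-To-Treat (ITT) analyses principles".

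Section 5.5.1 repeats the 30-day example but introduces it permissively: "The PI's study team may withdraw a patient participant from the study if". Section 7.2 also states the withdrawal. After withdrawal, section 5.5.2 allows routine care "but additional study data will not be collected", and section 7.6 likewise ends recording. Data gathered beforehand stay in the ITT analysis (sections 5.5.2 and 7.6).

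Section 12.4 defines ITT so that "all participants who provide data at baseline will retain their original assignment regardless of the treatment received". Its missing-data paragraph promises to seek follow-up information on every participant whether or not they completed the protocol. It then says that missing outcomes are not imputed.

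**The concern.** By the time the rule applies, the participant has been randomised (section 5.4.1), has taken the loading dose and has had at least one quadrant treated (section 6.7). The reason for removal is a scheduling failure after randomisation, not refusal of consent or loss of contact. Anyone who is still willing and reachable could supply both follow-up assessments, but the plan tells the study not to collect them.

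The plan handles comparable cases the other way. Participants who stop the drug (sections 5.5.2 and 6.3), are found ineligible (section 5.5.1) or become pregnant during treatment (section 9.4.3) may or will stay in the study. Section 5.5.1 already has a category for stopping the intervention while remaining enrolled and providing data. Late SRP is not placed in it.

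At stake is the completeness of the 6-week and 12-month comparisons. Safety capture is also shortened, because section 9.2 ties it to the last day of participation plus 7 days, or 30 days for serious events.

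**Working it through.** **Lateness.** The clock starts at first dose, which is given at the first baseline visit. The target is 10 days and removal follows day 30, so removal begins about 30 - 10 = 20 days after the due date.

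**What the analyses lose.**
- Probing depth (section 12.4): the mixed model has indicators for 6 weeks and 12 months and their interactions with arm. A removed participant supplies baseline rows only, with no direct information on either follow-up comparison.
- Remission (section 12.4): fitted separately at each follow-up visit with no imputation. A removed participant leaves this analysis entirely.
- Tipping-point analysis (section 12.4): run only if more than 5% of outcomes are missing and the study is positive. With less missingness, or a result that is not positive, this check is not made.

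**The plan's sample size.** Section 12.2 requires 220 per arm for 90% power at a 0.2 mm difference, allows 20% dropout, and spreads recruitment over 34 practitioners.
- 220 / 0.8 = 275 per arm, 550 in total.
- 34 x 16 = 544, or 272 per arm. The stated size reproduces to within 1.1%.
- 272 x 0.8 = 217.6 expected per arm. The 2.4 short of 220 comes from rounding to 34 x 16, not from the 30-day rule.

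**Power cost.** The 220 comes from a site-level simulation whose correlations are not given, so I back-solved a participant-level SD from the stated result (two-sided alpha 0.05):

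SD = 0.2 / [(1.960 + 1.282) x sqrt(2/220)] = 0.647 mm.

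Power = Phi(0.2 / [0.647 x sqrt(2/n)] - 1.960), with n = 272 x (1 - 0.20 - w). Here w is the share of randomised participants removed by the rule in addition to the 20%. The protocol gives no value for w; those below are assumptions.

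| w | Participants (w x 544) | n per arm | Power |
|---|---|---|---|
| 0 | 0 | 217.6 | 89.7% |
| 2% | 10.9 | 212.2 | 88.9% |
| 5% | 27.2 | 204.0 | 87.7% |
| 10% | 54.4 | 190.4 | 85.4% |
| 15% | 81.6 | 176.8 | 82.8% |

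**Bias, as an illustration.** Suppose removed participants improve d mm less than those retained, in both arms, and shares pA (active) and pP (placebo) are removed. The contrast among those retained then shifts by (pA - pP) x d.
- 5% in each arm: shift 0 for any d.
- 3% v 7%: (0.03 - 0.07) x 0.2 = -0.008 mm; with d = 0.5, -0.020 mm.
- 2% v 10%: (0.02 - 0.10) x 0.2 = -0.016 mm; with d = 0.5, -0.040 mm.

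Swapping the arms reverses the sign. All of these shares and values of d are assumed. The target difference is 0.2 mm.

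**The case against.** The strongest reply is that ITT survives as the protocol defines it. Nobody changes arm, baseline data stay in, and a likelihood-based mixed model can use those rows if data are missing at random. That is correct. A reader might infer that the rule contradicts the ITT analysis outright; sections 5.5.2, 7.6 and 12.4 do not support that.

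A reader might also infer that removal depends on arm, for example because drug side effects delay the visit. Section 9.3.2 lists nausea and allergic reaction as expected events, so this is possible, but nothing shows it. The cut-off is the same in both arms, practice staff are blinded, and the 10-day course leaves about 20 days in which to attend.

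Nor is the study shown to be underpowered. Only participants who need a second visit are exposed, the 20% allowance may already cover them, and section 12.2 reports power above 80% under moderate departures from its correlation and tooth assumptions.

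This is also not the only group withdrawn: section 5.5.1 lists people who cannot be contacted or have moved. But their outcomes usually cannot be obtained, whereas those of a late attender often can.

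Finally, the promise of follow-up in section 12.4 is paired with censoring at dropout. That does not resolve the conflict, because here the study itself imposes the dropout.

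These replies limit the size of the problem. They do not justify ending outcome collection for a reachable participant.

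**Conclusion.** The point holds as one of avoidable missing data. The protocol withdraws randomised, dosed and partly treated participants for an event after randomisation and stops collecting their outcomes. This undermines the ITT aim of sections 6.5 and 12.4 without formally contradicting it. It conflicts with the follow-up promised in section 12.4 and is out of line with how the plan treats other departures from the intervention. Sections 5.5.1 and 6.5 also disagree on whether withdrawal is optional or required, so practice could vary.

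The number affected is unknown. The power loss is about 1-2 points if 2-5% are lost beyond the planned 20%, and less if that allowance already includes them. Bias is zero when removal and the prognosis of those removed are alike in the two arms. In the illustrations above it is about 0.01-0.04 mm in size. The case for change rests on the loss being needless and cheap to prevent, not on a demonstrated large distortion.

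**What to change.** In sections 5.5.1, 6.5, 6.7 and 7.2, separate failure to complete the intervention from withdrawal from follow-up, using the category that section 5.5.1 already contains:

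- Record a second visit that is missing or later than 30 days as a protocol deviation.
- Keep the participant enrolled unless consent is withdrawn.
- Collect the scheduled 6-week and 12-month assessments and the safety data. State the date from which those visits are timed (for example the first baseline visit), since *post-intervention* is unclear when SRP is late or incomplete.
- Analyse as randomised.
- Reconcile the permissive wording of section 5.5.1 with the mandatory wording of section 6.5.

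The clinical handling of overdue SRP is for the sponsor to settle; nothing here changes a dose or a treatment interval.

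The cost is a short amendment in four places, using visits already in the schedule. The downside is a slightly more heterogeneous treated group.

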7 STUDY SCHEDULE

Practitioner Training

Node staff will provide practitioners with the study information and instructions including the patient participant selection procedures, methods for approaching patient participants and obtaining informed consent (according to regional approvals), methods for data collection, and other study procedures. In addition, NCs will conduct remote or in-person protocol training with practitioners and staff prior to initiating the study. The training ensures that the practitioner and staff understand the study procedures and receive instruction on the consent process, electronic data capture systems, safety event ascertainment, recording and reporting, and other relevant procedures. The NCs will maintain close contact with the practitioners prior to and throughout the study implementation period.

The study schedule will proceed in the following stages on a rolling basis:

- 1) Each participating Node will enroll practitioners into the study to obtain a total of approximately 34 across three participating nodes. A reasonable balance across Nodes is preferred but not required. For each of the three Nodes, participating practitioners will be enrolled over a period of approximately 4-6 months.
- 2) NCC will create randomization schedules and the PI's local study team will put together the IPPs based upon the randomization schedules created by the NCC and mail them to the practices.
- 3) Practitioners will complete activities to be deemed study ready.
- 4) Practices will screen and enroll eligible patient participants into the study.

7.1 Screening/Enrollment

Screening/Enrollment Visit (Visit 0, Day 0)

Prior to consent we will assess the following information that already exists and/or is generally collected as part of a standard of care dental appointment; this information may be used to aid in identifying a potential patient:

- Review medical/dental and medication history to determine initial eligibility based on the existing demographic data, medical health history (including vitals and medications)
- Existing radiographs to confirm periodontal bone loss
- Existing periodontal charting to assess periodontal status (if previous chart exists)

If a patient is identified as a possible candidate for the study, the practitioner and/or staff may introduce the study. At the screening examination consent must occur prior to data collection and the initiation of any study-specific procedures. The practitioner and potential patient participant will complete the screening process. Once the potential patient participant passes inclusion/exclusion criteria, the practitioner and / or trained practice staff will complete the consent process and HIPAA authorization with the patient and provide patient participants with copies of patient participant information and HIPAA authorization sheets. If the patient meets the criteria and accepts enrollment, the contact form and the Patient Participant Demographics form will then be completed via the electronic tablet.

Subsequently the practitioner will complete a periodontal examination with periodontal charting. If the practitioner only records the probe depths (PD), they should also collect gingival recession (GR) at the deepest probing site to help determine periodontal staging and grading, which is necessary to ascertain study eligibility. Guidance on periodontal staging and grading can be found in the training slides.

The following sequence of activities will take place at the screening visit after obtaining consent:

- Obtain patient participant contact information and preferred method of contact to include at least a cellular phone number, e-mail and postal mailing address along with an alternate method of contact (e.g., alternate postal mail, email, telephone,).
- Obtain demographic information, medical/dental history, medication history, alcohol, and tobacco use history.
- Record history of allergy to medications including antibiotics.
- Record full-mouth Probing Depth (PD) at 6 sites: mesiobuccal, buccal, distobuccal, mesiolingual, lingual, distolingual per tooth using a UNC-15 periodontal probe. PD will be recorded in the practitioner's electronic health record system.
- OPTIONAL: Record half-mouth (Upper right and Lower Left quadrants) Gingival Recession (GR) at 6 sites: mesiobuccal, buccal, distobuccal, mesiolingual, lingual, distolingual per tooth using a UNC-15 periodontal probe either at this screening or at the baseline visit. In the case that GR is not completed at screening, GR charting must be completed prior to SRP at the baseline visit (see baseline visit section).
- OPTIONAL: Record half-mouth (Upper right and Lower Left quadrants) Bleeding on Probing (BoP) at 6 sites: mesiobuccal, buccal, distobuccal, mesiolingual,

lingual, distolingual per tooth using a UNC-15 periodontal probe either at this screening or at the baseline visit. If time does not permit, completion at screening, BoP charting has to be completed prior to SRP at the baseline visit (see baseline visit section).

- Verify study eligibility status and schedule / perform baseline study visit for individuals who are eligible and available for the duration of the study.
- Provide patient participants with instructions needed to prepare for first study visit. Patient participants will be allowed to continue using their toothbrush and toothpaste of choice as recommended by their dental provider.

The patient participant will then be scheduled for the baseline study visit. However, if time permits, the baseline visit may be combined with screening visit.

7.2 Baseline

Baseline Visit (Visit 1, Day 0 + 30 days*)

- Randomize the patient participant by selecting next IPP packet and recording assignment in the EDC system. (NCC)
- Access IPP and randomized drugs/placebo. (Office staff / practitioner)
- Record the patient participant ID (PPT ID) on the IPP box label for future use and cross-check in the EDC system. (Office staff / practitioner)
- Practitioner provides patient participant with the drug/placebo loading dose (1g of each drug / placebo). (Practitioner). Recommended time is 30-60 minutes prior to procedure. The dental office personnel will monitor patient participants for any symptoms after receiving the first study medication dose for the duration of the dental appointment.
- Patient participant completes baseline OHIP-5. (Self-reported)
- Practitioner collects optional subgingival plaque specimen. (Practitioner)
- In case they were not collected at the screening visit, practitioner records periodontal measurements (Practitioner):

BoP will be recorded at 6-sites per tooth at half mouth using a prespecified half-mouth diagonal protocol and measured dichotomously as "0" (no bleeding), or "1" (bleeding).

Gingival Recession (GR) will be recorded at 6-sites per tooth at half mouth using a prespecified half-mouth diagonal protocol and measured from the CEJ to the gingival margin in mm. Areas of gingival overgrowth above the CEJ will be

recorded as negative ("-") recession (see training videos). Clinical attachment levels (CAL) will be indirectly calculated by the formula CAL=PD+GR.

- Administer anesthetic and perform mechanical debridement (SRP) intervention on all study patient participants. (Practitioner)
- Record adverse events as reported by patient participant or observed by practitioner. (Practitioner)
- Practitioner hands the antibiotics / placebo drug-safe vials to the patient participant and provides instructions to take one capsule from each bottle every 8 hours (q8h) until gone. (Practitioner)

If the intervention is not completed in one visit, the practitioners will be asked to complete treatment within 10 calendar days of the initial baseline visit in an optional second baseline visit (1B) where SRP will be performed in any remaining quadrants.

Second Baseline Visit (Visit 1B, Visit 1 + 10 days**)

Second baseline visit should occur within 10 days of the initial baseline visit. If the second baseline visit has not happened within

days from initiation of the investigational product (drug / placebo) the patient participant is withdrawn from the study.

- Administer anesthetic and perform remainder of mechanical debridement (SRP) intervention on all study patient participants.
- Instruct to continue taking the antibiotics / placebo as prescribed every 8 hours until gone.

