4.2 Patient participant recruitment

The patient participant population will be enrolled from National Dental PBRN practices without regard to sex, race, or ethnicity. Periodontitis diagnosis will follow the criteria established by the 2018 Classification of Peri-implant Diseases and Conditions. The study will enroll a target of N=544 adult patients aged 40 years, or older with an existing or new diagnosis of Generalized Stage II-III, Grade A-C periodontitis (previously Generalized Moderate to Severe Periodontitis) requiring periodontal treatment. At the time of screening periodontal status will be assessed to determine eligibility based on periodontal examination including probing depth, clinical attachment levels and patient participant characteristics, such as age, smoking and diabetic status according to the classification guidelines (Papapanou et al. 2018).

Intervention: Patient participants will receive conventional SRP (standard of care) with or without adjunctive antibiotics depending on group allocation (AMXM group versus Placebo group respectively). SRP refers to the procedure of mechanically debriding the root surfaces of teeth as part of periodontal treatment (Badersten et al. 1981). The SRP procedure will be provided by the PBRN practitioners or their practices' hygienists. All patient participants will receive SRP; either the entire mouth will be treated at the baseline visit (visit 1) or if determined by the practitioner a second optional baseline visit (visit 1B) may be scheduled within 10 days of visit 1 to complete the SRP. In conjunction with SRP, the patient participants will receive adjunctive AMXM or placebo as the study intervention based on randomized allocation. AMXM is a combination antibiotic comprised of Amoxicillin 500mg and Metronidazole 500mg in two separate capsules. The intervention will be administered in-office starting with a loading dose (1g Amoxicillin and 1g Metronidazole, i.e. two capsules of each medication, or equivalent placebo) of AMXM or placebo followed by a self-administered 10-day course (See Section 6.2). The AMXM or placebo will be provided to participating practitioners in Individual Patient participant Packages (IPPs), labeled and shipped to participating

practices by the Pl's local study team. The IPPs are packages containing all study supplies required for each patient participant including the study drugs, plaque collection supplies and shipping supplies (see MOP).

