6.1.2 Formulation, Packaging, and Labeling

6.1.2.1 Amoxicillin 500mg

Oakdell Pharmacy will procure Amoxil capsules, will empty the contents and then repackage the powder into non-identifiable green capsules that will match the placebo. The pharmacy will prepare 272 airtight drug-safe bottles containing 32 green capsules and will label them as bottle "A".

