6.2 Dosage, Preparation and Administration of Study Product

Study drugs will be formulated as capsules (green capsules for Amoxicillin 500mg and blue capsules for Metronidazole 500mg) and dispensed in two separate identical bottles, one of each drug (Bottle A and Bottle B, respectively) as mentioned above. Placebo capsules for Amoxicillin 500mg will be green, identical to the Amoxicillin 500mg capsules and Placebo capsules for Metronidazole 500mg will be blue, identical to the Metronidazole 500mg capsules, and will be dispensed in two separate bottles, similar to AMXM group to maintain care provider and patient participant masking. Two green capsules of Amoxicillin 500mg and two blue capsules of Metronidazole 500mg (AMXM group) or two green capsules of Placebo and two blue capsules of Placebo (Placebo group) will be given to the patient participants as a loading dose 30-60 minutes prior to initiation of the SRP procedure, because of evidence supporting greater benefit when antibiotics are given in conjunction with SRP (Kaner et al. 2007). A loading dose for the AMXM group will equate to 1g of Amoxicillin and 1g of Metronidazole. After the loading dose, each patient participant will be instructed to take one green capsule and one blue capsule every 8 hours for 10 days, in both AMXM and Placebo groups. Medication

bottles will not include any identifiers related to group allocation in order to maintain masking.

The identical labeling of the bottles between the two groups will ensure proper masking for the patient participants, the study staff, and practitioners administering the products.

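### Section 6.2 ends dosing at 10 days and Section 7.2 when the bottle is empty; after missed doses the second rule outlasts the 10-day avoidance advice in Section 6.6

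*Protocol*

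**What the plan says.** The protocol states the end of the course in two ways.

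- **By the calendar.** Section 6.2 tells participants, after the loading dose, to "take one green capsule and one blue capsule every 8 hours for 10 days". The protocol summary and Sections 2.2 and 4.2 also describe a 10-day course.
- **By the bottle.** Section 7.2 lists what the practitioner does at the visit. At visit 1 the practitioner hands over the vials with "instructions to take one capsule from each bottle every 8 hours (q8h) until gone". At the optional visit 1B the line is: "Instruct to continue taking the antibiotics / placebo as prescribed every 8 hours until gone". Neither line gives a day limit.

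On supply, Section 6.1.2.1 specifies "272 airtight drug-safe bottles containing 32 green capsules"; the metronidazole and placebo bottles also hold 32 each.

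On interacting drugs, Section 6.6 advises participants to "refrain from initiating a prohibited medication during the 10 days of the antibiotic intervention". It then says: "After the 10-day intervention, the risk of an adverse event from a concomitant medication is extremely low".

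The protocol text does not say whether a missed dose is to be made up after day 10 or left in the bottle.

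**The concern.** Section 6.6 sets the length of its advice by the calendar and judges the later risk on the premise that dosing is over. Section 7.2, which staff follow at the chair, ends dosing by the bottle. If the two end points separate, a participant who does as Section 7.2 says is still taking amoxicillin and metronidazole after the stated advice has run out.

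What is at stake is participant safety on a small scale. Section 6.6 itself names other antibiotics, alcohol, disulfiram and warfarin as interacting with the study drugs. The protocol also expects some capsules to be left over: Section 7.3 sends a day-10 text asking for a count and for the return of what remains, and Section 6.5 plans a count at 6 weeks.

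**Working it through.** **Inputs**

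- Capsules per bottle: 32 (Section 6.1.2).
- Loading dose: 2 capsules from each bottle, 1 g of each drug (Sections 4.2, 6.2 and 7.2). Section 2.2 mentions a 500 mg loading dose; the operational sections and the bottle count fit 1 g, which is used here.
- Schedule: one capsule from each bottle every 8 hours, so 24 / 8 = 3 a day.
- Missed doses: the protocol gives no figure, so a range is shown. Missed doses are assumed not to be doubled up.

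**Step 1: reproduce the supply.** 2 + 3 × 10 = 32 per bottle, the stated figure. After the loading dose 30 remain, due at hours 8, 16, …, 240. With full adherence both rules end at hour 240, which is day 10.

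**Step 2: add missed doses.** With m missed doses before day 10, m capsules remain in each bottle at hour 240. Under the bottle rule the last one is taken at hour 8 × (30 + m).

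| Missed doses (m) | Calendar rule ends | Bottle rule ends | Past the 10-day advice |
|---|---|---|---|
| 0 | 240 h | 240 h (day 10) | 0 h |
| 1 | 240 h | 248 h (day 10.3) | 8 h |
| 3 | 240 h | 264 h (day 11) | 24 h |
| 6 | 240 h | 288 h (day 12) | 48 h |

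**Step 3: express it as a rate.** If a constant share r of scheduled doses is missed, the expected time to empty the bottle is 10 / (1 − r) days. At assumed rates of 5%, 10%, 20% and 30% this is about day 10.5, 11.1, 12.5 and 14.3. If misses are independent, the chance of at least one among 30 doses is 1 − (1 − r)^30: 79% at 5% and 96% at 10%. These rates are illustrations, not estimates for this trial.

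**Step 4: set the results against Section 6.6.** Its advice on starting prohibited medications ends at day 10. Every row with m above zero leaves a period in which a participant following Section 7.2 is still dosing and that advice no longer applies.

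**The case against.** The strongest reply is that the two statements describe one prescription. The bottle is an exact 10-day supply, so the rules part only when a participant departs from the schedule. Other text leans towards a calendar end: the course is repeatedly called a 10-day one, the day-10 text asks for remaining capsules back, and Sections 6.4 and 6.5 provide for the return of leftovers. The written instructions that Section 8.1 says are dispensed are not shown and may contain a missed-dose rule.

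Much of this stands and keeps the point small. It does not remove it: visit 1 in Section 7.2 still tells the participant to finish the bottle, with no day limit.

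A reader might infer three stronger things that the documents do not support.

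- **That a late visit 1B restarts treatment.** Section 6.5 says: "Data may be collected within a 30-day time frame from initial medication dispensing, this will not be a protocol violation". That sentence concerns data collection and does not extend dosing. The visit 1B line speaks of continuing as prescribed, which does not naturally mean resuming a course already stopped. The schedule of events puts the visit on days 2 to 10, and Section 6.5 links that timing to antibiotic coverage. The wording would bear clarifying, but no overrun should be calculated from it.
- **That the conflict leaves new medications unrecorded.** Section 8.1 tracks only medication changes related to adverse events at any time after baseline, inside the 10 days as well as after them. That limit does not arise from the two stop rules.
- **That the advice on alcohol lapses at day 10.** The counselling on interactions in Section 6.6, which covers alcohol, has no stated end date. Only the sentence on starting a prohibited medication is tied to the 10 days.

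**Conclusion.** The inconsistency is real and minor. With full adherence there is no gap. Each missed dose that is not doubled up adds 8 hours, so 1, 3 or 6 missed doses carry the last capsule to day 10.3, 11 or 12. Over that stretch a participant in the active arm who follows Section 7.2 is on both antibiotics after the Section 6.6 advice against starting a prohibited medication has ended, and the premise for calling the later risk very low does not hold.

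Exposure is limited, because current users of interacting medication are excluded at entry. The instruction is the same in both arms and participants are analysed as randomized, so neither the intention-to-treat analysis nor the power is affected.

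The conclusion rests on the protocol text alone, on a 1 g loading dose, and on missed doses being taken later one at a time. How often the gap would occur cannot be judged, because the protocol gives no adherence figure.

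**What to change.** 1. **Section 6.6:** state that prohibited medications and alcohol are to be avoided for 10 days or until the participant's last dose, whichever is later. This change alone closes the safety gap under either stop rule.
2. **Sections 6.2 and 7.2:** use the same end-of-course wording. Either rule is acceptable. A calendar stop makes the capsules left over equal to the doses missed, but participants who miss doses take less drug (30 − 3 = 27 or 30 − 6 = 24 capsules per bottle with 3 or 6 missed). Finishing the bottle loses no drug but lengthens the course.
3. **Visit 1B in Section 7.2:** add that the instruction to continue applies only while the course is still running and does not mean restarting one that has ended.

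The cost is a few sentences in the protocol and a check that the dispensed instructions match. No new data are needed, and the sample size and analysis do not change.
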